### **8.2.4.2 Study Medication Discontinuation**

Study medication should be permanently discontinued in the event of any of the following:

- Severe infection requiring parenteral antimicrobial therapy or hospitalization
- Symptomatic herpes zoster
- Malignancy – except for non-melanoma skin cancer (e.g., squamous or basal cell carcinoma) not in or near the treatment area
- Anaphylactic or severe allergic reaction
- WBC Count:  $< 1 \times 10^9/L$  or second occurrence of  $< 2 \times 10^9/L$
- ANC:  $< 0.5 \times 10^9/L$  or second occurrence of  $< 1 \times 10^9/L$
- Lymphocyte count:  $< 0.3 \times 10^9/L$  or second occurrence of  $< 0.5 \times 10^9/L$
- Platelet count:  $< 50 \times 10^9/L$  or second event of  $< 75 \times 10^9/L$  - in each case, value should be confirmed by retesting before treatment discontinuation
- Hemoglobin:  $< 6.5 \text{ g/dL}$  or second occurrence of  $< 8 \text{ g/dL}$  - in each case, value should be confirmed by retesting before treatment discontinuation
- AST or ALT:
  - $> 5 \times \text{ULN}$  persisting for 1 week of study medication interruption or second event of  $> 5 \times \text{ULN}$
  - $> 3 \times \text{ULN}$  with total bilirubin  $> 2 \times \text{ULN}$  or symptoms of hepatocellular injury [fatigue, nausea, vomiting, right upper quadrant pain or tenderness, fever, rash and/ or eosinophilia ( $> 5\%$ )].
- Serum creatinine:  $> 2 \times \text{ULN}$  persisting for  $> 2$  weeks of treatment discontinuation or second occurrence of  $> 2 \times \text{ULN}$

The continued treatment of subjects who experience other serious or severe adverse events considered related to study treatment should be discussed with the Sponsor's medical monitor.

## **9. PREGNANCY**

### **9.1. Definition of Women of Child Bearing Potential (WOCBP)**

WOCBP includes any female who has experienced menarche and who has not undergone successful surgical sterilization (e.g., hysterectomy, bilateral tubal ligation, or bilateral oophorectomy) or is not postmenopausal. Postmenopausal is defined as  $\geq 12$  months with no menses without an alternative medical cause. WOCBP must have a negative serum pregnancy test at Screening (Visit 1) and a negative UPT at Baseline (Visit 2) prior to randomization and monthly throughout the study.

### **9.2. Highly Effective Methods of Birth Control**

The Investigator or subinvestigator will discuss the potential risk factors associated with pregnancy and the importance of maintaining a highly effective method of contraception throughout the study with all WOCBP (for example, those which result in a low failure rate - i.e., less than 1% per year-

when used consistently and correctly). All WOCBP must use a highly effective method of birth control during the study and for 30 days after the final application of study medication in a manner such that risk of failure is minimized.

Highly effective methods include:

- Combined (estrogen and progestogen containing) hormonal contraception associated with inhibition of ovulation:
  - oral
  - intravaginal
  - transdermal
- Progestogen-only hormonal contraception associated with inhibition of ovulation:
  - oral
  - injectable
  - implantable
- intrauterine device (IUD)
- Obstruction of fallopian tubes via medical device (EssureTM)
- intrauterine hormone-releasing system (IUS)
- vasectomized partner
- sexual abstinence

Vasectomized partner is a highly effective birth control method provided that partner is the sole sexual partner of the WOCBP trial participant and that the vasectomized partner has received medical assessment of the surgical success.

 Sexual abstinence is considered a highly effective method only if defined as refraining from heterosexual intercourse during the entire period of risk associated with the study treatments (study duration and 30 days after the last study medication application). The reliability of sexual abstinence needs to be evaluated in relation to the duration of the clinical trial and the preferred and usual lifestyle of the subject.

WOCBP must be on a highly effective method of birth control for the following timeframes prior to study entry:

- Implants (on a stable dose for  $\geq 90$  days)
- Injectables (on a stable dose for  $\geq 90$  days)
- Patches (on a stable dose for  $\geq 90$  days)
- Combined oral contraceptives (on a stable dose for  $\geq 90$  days)
- Intrauterine devices (inserted for  $\geq 30$  days)

Prior to trial enrollment, WOCBP must be advised of the importance of avoiding pregnancy during trial participation and of the potential risk factors associated with pregnancy while in study. The subject must sign an informed consent form documenting this discussion. During the trial, all WOCBP will be instructed to contact the investigator immediately if they suspect they might be pregnant (*e.g.*, missed or late menstrual period).

If a subject or investigator suspects that the subject may be pregnant prior to study medication administration, the study medication must be withheld until the results of a pregnancy test are available. If pregnancy is confirmed, the subject must not receive study medication and must be discharged from the study.

CONFIDENTIAL  
Page 48 of 57

If, following study medication administration, it is determined that the subject may have been or was pregnant at the time of study medication exposure (including at least 2 days after study medication administration) the investigator must immediately notify the Aclaris Therapeutics, Inc. Medical Monitor and record the event on a pregnancy surveillance form. While not an AE or SAE, the investigator must report every pregnancy using a pregnancy surveillance form and follow the reporting procedures described for SAE reporting as described in Section 8.2.2.

Protocol-required procedures for trial discontinuation and follow-up must be performed on the subject unless contraindicated by pregnancy (e.g., x-ray studies). Other appropriate pregnancy follow-up procedures should be considered if indicated. In addition, the investigator must report to Aclaris Therapeutics, Inc.'s Medical Monitor on the pregnancy surveillance form, follow-up information regarding the course of the pregnancy, including perinatal and neonatal outcome. Infants should be followed for a minimum of six weeks.

If the outcome of the pregnancy meets the criteria for an SAE (i.e., ectopic pregnancy, spontaneous abortion, intrauterine fetal demise, neonatal death, or congenital anomaly [in a live born, a terminated fetus, an intrauterine fetal demise, or a neonatal death]), the investigator should follow the procedures for reporting SAEs.

## **10. STATISTICAL ANALYSES**

### **10.1. Statistical Methods**

Summary descriptive statistics (N, mean, median, SD) by visit will be provided for all safety and efficacy parameters. Primary and secondary efficacy parameters are described below:

Mean change from baseline in eyebrow growth will be calculated as the mean change in the Clinician's Eyebrow Assessment (CEA) from Visit 2 (Baseline) compared to end of treatment (Visit 10). The CEA evaluates eyebrows on a scale from "No eyebrow hair" (grade 0) to "Full eyebrow hair" (grade 4).

Mean change from baseline in the Subject's Eyebrow Assessment (SEA) will be calculated from Visit 2 (Baseline) to end of treatment (Visit 10).

Mean change from baseline in the Subject's Eyebrow Satisfaction (SES) will be calculated from Visit 2 (Baseline) to end of treatment (Visit 10).

All efficacy summaries will be based on the per-protocol population including all subjects who have Baseline (Visit 2) and Visit 10 efficacy data and no major protocol violations.

Safety analyses will include descriptive statistics calculated on the safety parameters using the safety population. The proportion of subjects with treatment-emergent adverse events will be tabulated and presented by Medical Dictionary for Regulatory Activities (MedDRA) System Organ Class. Vital signs and clinically significant abnormal laboratory results will also be

CONFIDENTIAL  
Page 49 of 57

tabulated and presented. Change from baseline in the Local Tolerability Assessments (LTA) to end of treatment (Visit 10) will be summarized.

Data from all enrolled and treated subjects will be presented and summarized. Safety summaries will include listings by study medication of adverse events incidences within each MedDRA System Organ Class, and changes from pre-application values in vital signs. Adverse event summaries will be presented by study medication showing the proportion of subjects experiencing adverse events, both overall and by MedDRA System Organ Class.

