## 2. LIST OF ABBREVIATIONS AND DEFINITIONS OF TERMS

Abbreviation	Term
AA	Alopecia Areata
AE	Adverse Event
ALT	Alanine aminotransferase
ANCOVA	Analysis of Covariance
ANOVA	Analysis of Variance
AST	Aspartate aminotransferase
AT	Alopecia Totalis
AU	Alopecia Universalis
BID	Twice-daily
BUN	Blood Urea Nitrogen
°C	Degrees Centigrade
CD	Cluster of Differentiation
CEA	Clinician's Eyebrow Assessment
CMV	Cytomegalovirus
CRA	Clinical Research Associate
CRF	Case Report Form
CS	Clinically Significant
DMARDs	Disease modifying anti-rheumatic drugs
DPCP	Diphenylcycloprophenone
e.g.	for example (Latin; exempla gratia )
EC	Ethics Committee
ECG	Electrocardiogram
eCRF	Electronic Case Report Form
EHL	Eyebrow Hair Loss
°F	Degrees Fahrenheit
FDA	Food and Drug Administration
G	Gram
GCP	Good Clinical Practice
HEENT	Head, Eye, Ear, Nose and Throat
HIPAA	Health Insurance Portability and Accountability Act of 1996
HIV	Human Immunodeficiency Virus
IB	Investigator's Brochure
ICF	Informed Consent Form

CONFIDENTIAL  
Page 13 of 57

Abbreviation	Term
ICH	International Conference on Harmonization
i.e.	that is (Latin; id est)
IFN	Interferon
IL	Interleukin
IRB	Institutional Review Board
IUD	Intrauterine Device
IUS	Intrauterine Hormone Releasing System
JAK	Janus Kinase
LDH	Lactate Dehydrogenase
LTA	Local Tolerability Assessment
LOCF	Last Observation Carried Forward
MedDRA	Medical Dictionary for Regulatory Activities
MHC	Major Histocompatibility Complex
ml	Milliliter
Mm	Millimeter
NCS	Not Clinically Significant
NK/ NKG	Natural Killer/ Natural Killer Group
OTC	Over-The-Counter
PDT	Photodynamic Therapy
PUVA	Psoralen and Ultraviolet A
SADBE	Squaric acid dibutyl ester
SAE	Serious Adverse Event
SEA	Subject's Eyebrow Assessment
SES	Subject's Eyebrow Satisfaction
SI	Subject Identifier
SOP	Standard Operation Procedure
STAT	Signal Transducer and Activator of Transcription
TEAE	Treatment Emergent Adverse Event
Tyk2	Tyrosine Kinase 2
UPT	Urine Pregnancy Test
US	United States
UVA	Ultraviolet A
UVB	Ultraviolet B
WOCBP	Women of childbearing potential

CONFIDENTIAL  
Page 14 of 57

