### **5.5.2. Prohibited therapies**

Any medication or over-the-counter product known to affect hair growth is prohibited throughout the study period. Any prescription topical retinoids, over-the-counter topical products containing retinol, alpha hydroxy acids (e.g. glycolic, lactic acids) and beta hydroxy acids (e.g. salicylic acid) or cosmetic procedures applied to or in close proximity around the eyebrow area that in the opinion of the investigator may affect the safety or efficacy of the subject are prohibited throughout the study. New eyebrow tattooing, microblading, or piercing is not allowed during the study. During this study, subjects are prohibited from using therapies listed in the exclusion criteria. The investigator should notify the Medical Monitor, if any prohibited therapies are required to ensure subject safety.

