## **5.6. Subject Discontinuation from the Study**

Subjects will be informed that they are free to withdraw from the study at any time and for any reason. The Investigator may remove a subject from the study if, in the Investigator's opinion, it is not in the best interest of the subject to continue the study. Examples of other reasons subjects may be discontinued from the study are: a change in compliance with an inclusion or exclusion criterion, occurrence of AEs, occurrence of pregnancy, or use of a prohibited therapy. Notification of discontinuation will immediately (within 24 hours) be made to the Aclaris Therapeutics, Inc. study monitor.

In case of premature discontinuation of study participation, efforts will be made to perform all final study day assessments. The date the subject is withdrawn from the study and the reason for discontinuation will be recorded in the subject's source documents and on his/her case report forms (eCRFs). All withdrawn subjects with ongoing AEs will be followed as specified in section 8.2.1 of this protocol.

The study may be discontinued at the discretion of Aclaris Therapeutics, Inc. Some examples of reasons for discontinuation are the occurrence of the following:

- Increased frequency, severity or duration of known AEs
- Medical, business, regulatory or ethical reasons affecting the continued performance of the study
- Difficulties in the recruitment of subjects

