### 7.1.1. Clinician's Eyebrow Assessment (CEA)

The CEA is the investigator's assessment of the affected area of the eyebrow(s) at a particular point in time. The investigator should NOT refer to any other assessments to assist with these assessments.

At Visits 1, 2 and 5-11, the investigator or designee will assess the affected area of the eyebrow(s) using the scale below and report the one integer that best describes the amount of eyebrow hair present. If both eyebrows are affected, each eyebrow should be evaluated separately:

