### 7.1.3. Subject Eyebrow Satisfaction (SES)

The SES is the subject's assessment of her/his satisfaction with the status of the affected eyebrow(s), relative to the amount of hair present, at a particular point in time. The subject should NOT refer to any other assessments to assist with these assessments.

At Visits 2, 7, 10 and 11, the subject will assess the affected eyebrow(s) using the scale below and report the one integer that best describes her/his satisfaction with the status of the affected eyebrow(s). If both eyebrows are affected, each eyebrow should be evaluated separately:

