### **12.4. Study Conduct and Protocol Amendments**

With the exception of eliminating an immediate hazard to a subject, the investigator should not deviate from the protocol or implement any changes without prior written approval from Aclaris Therapeutics, Inc. and prior review and documented approval from the IRB/EC.

Changes that involve only logistical or administrative changes are allowed. The investigator should document and explain any deviation from the protocol. A protocol deviation is a non-adherence to protocol-specific study procedures or schedules that does not increase the risk to a study subject and does not affect the scientific integrity of the study.

A protocol violation is defined as any divergence from the protocol-specific study procedures or schedules that may result in an increased risk to a study subject or that affect the scientific integrity of the study. All protocol violations must be reviewed by the Medical Monitor and reported to the IRB by the Investigator, as directed by the IRB-specific procedures.

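### Efficacy is summarised only in per-protocol subjects with Visit 10 data; no all-treated efficacy summary is clearly specified, and the place of early-termination assessments is not stated

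*Combined protocol and SAP*

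**What the plan says.** The synopsis (Statistical Methods) and section 10.1 carry the same rule: "All efficacy summaries will be based on the per-protocol population including all subjects who have Baseline (Visit 2) and Visit 10 efficacy data". Freedom from major protocol violations is a further condition. Section 10.1 also promises N, mean, median and SD by visit for the efficacy parameters, and takes change in the CEA, SEA and SES from Visit 2 to Visit 10.

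Later in section 10.1 comes a general sentence: "Data from all enrolled and treated subjects will be presented and summarized". It does not name efficacy, and the text before and after it concerns safety.

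On leavers, section 5.6 says: "In case of premature discontinuation of study participation, efforts will be made to perform all final study day assessments". Neither that section nor section 10.1 says how such readings are analysed. Section 6.3.4 places Visit 10 at 24 weeks, plus or minus 4 days, and the final study day could equally be read as Visit 11. The abbreviation list in section 2 contains "Last Observation Carried Forward", but no analysis text that I could read applies it.

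Section 5.8 rules out replacing non-completers. Section 12.4 begins its definition "A protocol violation is defined as any divergence from the protocol-specific study procedures or schedules" and limits it to divergences that may raise risk or affect scientific integrity. It does not say what makes a violation major. Section 11.3 has evaluability settled before database lock.

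For the CEA, section 7.1.1 says: "At Visits 1, 2 and 5-11, the investigator or designee will assess the affected area of the eyebrow(s) using the scale below". Section 7.1.2 gives the SEA the same visits. For the SES, section 7.1.3 says: "At Visits 2, 7, 10 and 11, the subject will assess the affected eyebrow(s) using the scale below".

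**The concern.** Whether a subject is counted for efficacy depends on what happens after the first application. Some routes out may be linked to treatment: adverse events (section 5.6), being unable to keep up twice-daily application for more than 4 consecutive days (section 6.6.8), or listed ECG findings (section 8.2.3). Those who remain may therefore differ in regrowth from those who were treated.

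Efficacy is part of the main objective (section 4), and section 3.2 describes the purpose as demonstrating it. With no control arm, the single-arm mean change carries that result, and with about 12 subjects one or two exclusions can move it. The plan offers no clear second summary that would show the size or sign of the effect.

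The silence on early-termination readings adds to this. Two analysts following section 10.1 could build different populations from the same data.

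**Working it through.** The plan states no dropout rate, effect size, SD, alpha or power (section 10.2 says there is no formal power calculation), so there is no figure of its own to reproduce. What can be done is to count what a leaver loses and to bound the mean.

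**Readings lost by an early leaver, if early-termination assessments do not count as Visit 10**

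- CEA and SEA: the scheduled post-baseline visits before Visit 10 are Visits 5 to 9 (Weeks 4, 8, 12, 16 and 20). That is 0 to 5 readings on each scale, depending on when the subject leaves.
- SES: only Visit 7 (Week 12) falls between baseline and Visit 10, so 0 or 1 reading.
- The restriction covers all efficacy summaries, so these readings leave the by-visit tables as well as the Visit 10 comparison.

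If early-termination assessments do count as Visit 10, leavers who have one and no major violation stay in.

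**Bounds on the all-treated mean CEA change**

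Inputs from the documents: N = 12 (section 5.1, approximate); CEA range 0 to 4 (section 7.1.1); baseline grade 0 in at least one eyebrow (section 5.3). Assumptions: one score per subject, starting at 0, so that change lies between 0 and +4; d subjects lost; completer mean m; mean change x in those lost.

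All-treated mean M = [(12 − d)m + d·x] / 12

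Reported mean minus all-treated mean = m − M = d(m − x) / 12

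| m (assumed) | d = 1, x = 0 to 4 | d = 2, x = 0 to 4 |
|---|---|---|
| 0.5 | 5.5/12 = 0.46 to 9.5/12 = 0.79 | 5/12 = 0.42 to 13/12 = 1.08 |
| 1.0 | 11/12 = 0.92 to 15/12 = 1.25 | 10/12 = 0.83 to 18/12 = 1.50 |
| 2.0 | 22/12 = 1.83 to 26/12 = 2.17 | 20/12 = 1.67 to 28/12 = 2.33 |

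At m = 1.0 the difference m − M runs from (1 − 4)/12 = −0.25 to 1/12 = +0.08 with one lost, and from 2(1 − 4)/12 = −0.50 to 2/12 = +0.17 with two lost. The sign is that of m − x: the reported mean is too high if those lost regrew less than those kept, and too low if they regrew more. The documents do not fix x.

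**Why a single imputation would not do**

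Take one leaver last seen at +3 in Week 20, with 11 completers at a mean of 1.0. Setting the missing change to 0 gives 11/12 = 0.92. Using the last observed value gives (11 + 3)/12 = 1.17. The best possible score gives (11 + 4)/12 = 1.25. Zero change alone would ignore regrowth that had been seen, and for an eyebrow starting at 0 it can never raise the CEA mean.

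**The case against.** The strongest reply is one of proportion. This is an open-label pilot with descriptive statistics, no hypothesis test and no decision threshold in the text. The sizes above rest wholly on an assumed number lost and an assumed mean, and vanish if everyone completes without a major violation. That stands, and it limits the weight of the point.

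Second, the sentence on all enrolled and treated subjects opens its own paragraph and could be read to cover efficacy. That reading is available, so a reader who infers that the plan rules out any all-treated efficacy display goes too far. But the sentence does not name efficacy and cannot clearly override a rule that covers all efficacy summaries.

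Third, there are some safeguards. Section 12.4 separates violations from deviations that affect neither risk nor scientific integrity, and has the Medical Monitor review all violations. Section 11.3 settles evaluability before lock. This counts against inferring that exclusions will be chosen with an eye to outcome; the documents do not say so. Because the study is open-label, however, the pre-lock step is not a blinded safeguard.

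Fourth, excluding some subjects is defensible. Section 5.5.2 states: "Any medication or over-the-counter product known to affect hair growth is prohibited throughout the study period". Regrowth in a user of such a product is confounded. Dropping that subject may put the reported mean below the all-treated mean, but it does not show that the drug's effect is understated.

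Finally, the flow chart in section 6.2 was only partly legible in the copy I read, so a note there on early termination should be looked for. What section 10.1 itself leaves open is unaffected.

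**Conclusion.** The concern holds in a limited form. The plan restricts every efficacy summary to subjects selected on events after treatment began, specifies no clear all-treated counterpart, and does not say where early-termination readings belong. The reported mean change may be biased in either direction.

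A reader might infer that the mean will be overstated, since people who see no regrowth may be more likely to leave. That is plausible, but the documents give neither a dropout rate nor outcomes for leavers, so the direction is not established. Nor does the entry in the abbreviation list show that a carry-forward rule was intended.

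On size, at an assumed completer mean of 1.0, the all-treated mean lies within 0.92 to 1.25 (one of 12 lost) or 0.83 to 1.50 (two lost). These are limits, not likely values. They assume one score per subject starting at grade 0. Sections 7.1.1 to 7.1.3 score affected eyebrows separately, so counting eyebrows would change the weights. No error rate or power is affected. Severity is modest, but the correction is cheap and worth making.

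**What to change.** Amend section 10.1 and the matching synopsis text as follows.

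1. Make the main efficacy summary all subjects who applied study medication and have a baseline assessment, using observed data by visit with N at each visit. Keep the per-protocol summary as supportive, with both Ns side by side, and word the general sentence on enrolled and treated subjects to agree.
2. Report early-termination assessments in their own row, not as Week 24 values in the main summary. Section 3.1 notes that patchy loss can come and go, so an earlier reading need not stand for Week 24.
3. Observed data alone do not supply a leaver's Visit 10 value. As a sensitivity analysis, show the all-treated Visit 10 mean with missing values set in turn to no change from baseline, the last observed value, and the best and worst possible scores. For a CEA eyebrow starting at 0, no change and worst score coincide. They need not for the SES, where 1 is best and 7 worst.
4. Flag readings taken after use of a prohibited hair-growth product, show the all-treated summary with and without them, and list each subject excluded from the per-protocol population with the reason.

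The cost is wording and a few more table rows and columns, with no new visits or data. The reported mean may turn out less favourable.

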## **4. STUDY OBJECTIVES**

The main objective of this study is to assess the safety, tolerability and efficacy of ATI-50002 Topical Solution 0.46% in subjects with unilateral or bilateral loss of eyebrow hair due to AA, AU or AT.

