## **5. SELECTION AND DISPOSITION OF STUDY POPULATION**

### **5.1. Number of Subjects**

Approximately 12 subjects will be enrolled at 1 to 2 sites in the United States.

CONFIDENTIAL  
Page 18 of 57

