### **7.2.5. Local Tolerability Assessment (LTA)**

The LTA is the investigator's assessment of the average overall severity of signs and the subject's assessment of the average overall severity of symptoms associated with irritation on each eyebrow considered separately. The investigator and subject must NOT refer to any other evaluation to assist with these assessments. This is not a comparison with the assessment at any other time point.

At Visits 2-11, the investigator and the subject will evaluate the LTA signs and the LTA symptoms respectively.

LTA Signs (assessed by the investigator for each eyebrow separately):

- Erythema
- Edema
- Scaling/dryness

LTA symptoms (assessed by the subject for each eyebrow separately):

- Stinging
- Burning

The investigator will assess the LTA signs as follows:

- At Visit 2:
  - Prior to the first study medication application
  - 20 ( $\pm 4$ ) minutes after the application completion time.
- At Visits 3-11

CONFIDENTIAL  
Page 39 of 57

The subject will assess the LTA symptoms as follows:

- At Visit 2:
  - Prior to the first study medication application report the LTA for each symptom over the previous 24 hours
  - 10 ( $\pm 4$ ) minutes after the application completion time report the average severity since the application completion time
- At Visits 3-11:
  - Report the average LTA for each symptom over the previous 24 hours

The investigator, for the signs, should report the one integer that best describes the average overall severity on each eyebrow separately using the scales below:

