#### 8.1.5. Relationship to study medication

The investigator will determine if there is a reasonable causal relationship between the study medication and an AE or not. The investigator will use her/his best medical judgment and consider all relevant factors (e.g., temporal relationship, location of the event, the subject's relevant medical history, concomitant therapies and concurrent conditions) to determine the relationship of the AE to the study medication. The investigator will define the relationship of an AE to the study medication by selecting one of the following categories:

**Related** – There is a reasonable possibility that there is a causal relationship between the study medication and the AE.

**Not Related** – There is not a reasonable possibility that there is a causal relationship between the study medication and the AE.

The term “reasonable causal relationship” means there are facts or arguments to suggest a causal relationship (International Conference on Harmonization (ICH) E2A).

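### The planned local tolerability summaries cannot show how many different subjects ever had moderate or severe irritation

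*Combined protocol and SAP*

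**What the plan says.** Section 4 puts tolerability beside safety and efficacy in the main objective. Section 7.2.5 sets the measurement: "At Visits 2-11, the investigator and the subject will evaluate the LTA signs and the LTA symptoms respectively". The investigator grades three signs (erythema, edema, scaling/dryness) and the subject grades two symptoms (stinging, burning). Each is scored 0 to 3, separately for each eyebrow. At Visit 2 there is one assessment before and one after the first application. At Visits 3 to 11 the symptom score is an average over the preceding 24 hours.

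Section 10.1 gives the analysis in two sentences. The general one is "Summary descriptive statistics (N, mean, median, SD) by visit will be provided for all safety and efficacy parameters". The specific one is "Change from baseline in the Local Tolerability Assessments (LTA) to end of treatment (Visit 10) will be summarized". The Synopsis says the same. Section 10.1 also states in general terms that data from all enrolled and treated subjects will be presented and summarized, without naming an LTA output.

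Neither place plans grade frequencies, a worst grade per subject, or a count of subjects reaching grade 2 or 3. Neither says how two separately scored eyebrows are combined.

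**The concern.** Local irritation from a topical product may come and go. The usual question is how many subjects had it and how bad it became. A change from baseline to one late visit answers something else: whether irritation is present at the end. By-visit means and SDs describe each visit as a separate cross-section and lose track of individuals.

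At stake is the tolerability conclusion. With about 12 subjects in one arm, the number ever affected is the simplest result the study can give on this part of its objective, and no planned statistic provides it. The gap does not depend on drop-out. It exists even if every subject completes Visit 10.

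**Working it through.** **Inputs.** Section 5.1: "Approximately 12 subjects will be enrolled at 1 to 2 sites in the United States". The scale is the integers 0 to 3 (Section 7.2.5). There are eight on-treatment, post-application times before Visit 10: Visit 2 post-application and Visits 3 to 9. The plan states no tolerability figure to reproduce. The irritation pattern is my assumption: k of 12 subjects each have one grade 3 score at one of the eight times and grade 0 otherwise, including before application and at Visit 10.

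**1. Change to Visit 10.** Every subject goes from 0 to 0, so the mean change is 0.00 for k = 3, 6, 9 or 12.

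**2. One visit.** Variance = (sum of squares − n × mean²)/(n − 1), with n = 12. Three patterns give a mean of 3/12 = 0.25 and a median of 0:
- one grade 3: (9 − 0.75)/11 = 0.75, SD 0.87
- one grade 2 and one grade 1: (5 − 0.75)/11 = 0.386, SD 0.62
- three grade 1: (3 − 0.75)/11 = 0.205, SD 0.45

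Here the SD identifies the severe score. That is not always so. Three subjects at grade 2 have sum 6 and sum of squares 12. One subject at grade 3 with three at grade 1 also has sum 6 and sum of squares 9 + 3 = 12. Both give N 12, mean 0.50, median 0 and SD √((12 − 3)/11) = 0.90, yet one pattern contains a severe score and the other does not.

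**3. Across visits.** Suppose six visits each show mean 0.25, SD 0.87 and median 0, so each has exactly one severe score. Six subjects with one severe score each produce these rows. So does one subject who is severe at all six visits. The number ever severe could be anything from 1/12 = 8% to 6/12 = 50%.

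**4. Effect of timing, k = 6.** Each subject reacting at a visit adds 3/12 = 0.25 to its mean.
- Evenly staggered: highest visit mean 0.25.
- Random over eight times: of 8⁶ = 262,144 equally likely arrangements, the largest number of subjects sharing a time is 1, 2, 3, 4, 5 or 6 in 20,160, 181,440, 54,320, 5,880, 336 and 8 of them. The expected maximum is 571,248/262,144 = 2.18 subjects, so the highest visit mean averages 2.18 × 0.25 = 0.54. A simulation of 100,000 draws also gave 0.54. The fully staggered case has probability 20,160/262,144 = 8%.
- All at one visit: 6 × 0.25 = 1.5.

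With all 12 ever severe, the highest visit mean is 0.50 if evenly staggered, averages 0.86 if random, and is 3.0 if all coincide.

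**5. Per-subject count in the same data.** 3/12 = 25% (exact 95% CI 5.5% to 57.2%), 6/12 = 50% (21.1% to 78.9%) and 12/12 = 100% (73.5% to 100%), whatever the timing.

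**The case against.** The best defence is that the planned output is more informative than its means suggest. In the staggered example a mean of 0.25 with SD 0.87 and N 12 can only be one grade 3 and eleven grade 0, so a careful reader sees a severe score at each affected visit. Staggering is also the most favourable case for dilution. Reactions to the first application would fall together at the Visit 2 post-application assessment, where six of them give a mean of 1.5. These points stand, and they limit the concern to what the by-visit figures cannot do: count subjects across visits and, in some patterns, separate severe from moderate scores.

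Irritation may also surface elsewhere. Adverse events are defined broadly (Section 8.1.1), application changes go on the eCRF (Section 6.6.8), safety is reviewed monthly (Section 7.2), and the general promise to present data from all treated subjects may produce listings. This makes it less likely that poor tolerability goes unnoticed. But no rule ties an LTA grade to adverse event reporting, no LTA listing is named, and a listing is not a summary.

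A reader might go further and infer that the adverse event tables hide treatment-area reactions because they are planned by System Organ Class. Section 10.1 does not support that. It plans "Adverse event summaries will be presented by study medication showing the proportion of subjects experiencing adverse events, both overall and by MedDRA System Organ Class", so an overall proportion is included, and its account of what safety summaries include is not worded as exhaustive. Tables by preferred term, severity and relationship are reporting detail, not a separate fault.

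Finally, a bare worst-grade table has weaknesses of its own. It would count signs present before treatment, it needs a rule for two eyebrows, and it misses symptoms outside the 24-hour recall. These points are right, and the fix below allows for them.

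**Conclusion.** The concern holds in a limited form. The Visit 10 change carries no information on irritation that has resolved. The by-visit statistics can hint at severe scores but do not give the number of subjects ever affected. In the example with 6 of 12 ever severe, the highest visit mean ranges from 0.25 to 1.5 according to timing, while the per-subject figure is 50% throughout.

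This rests on the assumed pattern of single, resolving grade 3 reactions. The documents do not say how often or when irritation occurs.

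A reader might infer that the tables could present a poorly tolerated solution as causing essentially no irritation at any visit. That is too strong. The planned SD exposes isolated severe scores in the staggered case, and reactions shared at one visit show plainly in the mean. The defect is a missing per-subject count for part of the main objective in a small descriptive pilot. It can be corrected at the reporting stage without touching study conduct.

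**What to change.** Keep the planned Visit 10 change and by-visit statistics. For each LTA sign and symptom, in all treated subjects, add to Section 10.1:

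- n (%) of subjects by grade at each time point, with Visit 2 pre-application and post-application shown separately;
- n (%) of subjects by worst post-application grade, from Visit 2 post-application to Visit 10, cross-tabulated against the pre-application grade as a shift table, so that pre-existing signs are not counted as reactions;
- Visit 11, which is off treatment, shown separately.

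Use treated eyebrows only, and take the worse eyebrow when both are treated. Add a footnote that symptom scores at Visits 3 to 11 cover only the previous 24 hours, so the worst-grade table is a lower bound on transient symptoms.

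No new data, visits or subjects are needed. The cost is a few extra tables and a possibly less favourable tolerability figure.
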